8.2.4. Hospitalization

Hospitalization is defined as any initial admission (even less than 24 hours) in a hospital or equivalent healthcare facility, or any prolongation of an existing admission. Admission also includes transfer within the hospital to an acute/intensive care unit (eg, from the psychiatric wing to a medical floor, medical floor to a coronary care unit, or neurological floor to a tuberculosis unit). An emergency room visit does not necessarily constitute a hospitalization; however, the event leading to the emergency room visit is assessed for medical importance.

Hospitalization does not include the following:

- Rehabilitation facilities;
- Hospice facilities;
- Respite care (eg, caregiver relief);
- Skilled nursing facilities;
- Nursing homes;
- Same-day surgeries (as outpatient/same-day/ambulatory procedures).

Hospitalization or prolongation of hospitalization in the absence of a precipitating clinical AE is not in itself an SAE. Examples include:

- Admission for treatment of a preexisting condition not associated with the development of a new AE or with a worsening of the preexisting condition (eg, for workup of a persistent pretreatment laboratory abnormality);
- Social admission (eg, subject has no place to sleep);

- Administrative admission (eg, for yearly physical examination);
- Protocol-specified admission during a study (eg, for a procedure required by the study protocol);
- Optional admission not associated with a precipitating clinical AE (eg, for elective cosmetic surgery);
- Hospitalization for observation without a medical AE;
- Preplanned treatments or surgical procedures. These should be noted in the baseline documentation for the entire protocol and/or for the individual subject.

Diagnostic and therapeutic noninvasive and invasive procedures, such as surgery, should not be reported as SAEs. However, the medical condition for which the procedure was performed should be reported if it meets the definition of an SAE. For example, an acute appendicitis that begins during the reporting period should be reported if the SAE requirements are met, and the resulting appendectomy should be recorded as treatment of the AE.

8.3. Severity Assessment

If required on the AE page of the CRF, the investigator will use the adjectives MILD, MODERATE, or SEVERE to describe the maximum intensity of the AE. For purposes of consistency, these intensity grades are defined as follows:

MILD	Does not interfere with subject's usual function.
MODERATE	Interferes to some extent with subject's usual function.
SEVERE	Interferes significantly with subject's usual function.

Note the distinction between the severity and the seriousness of an AE. A severe event is not necessarily an SAE. For example, a headache may be severe (interferes significantly with the subject's usual function) but would not be classified as serious unless it met one of the criteria for SAEs, listed above.

8.4. Special Situations

8.4.1. Protocol-Specified Serious Adverse Events

There are no protocol specified SAEs in this study. All SAEs will be reported to Pfizer safety by the investigator as described in previous sections, and will be handled as SAEs in the safety database.

8.4.2. Potential Cases of Drug-Induced Liver Injury

Humans exposed to a drug who show no sign of liver injury (as determined by elevations in transaminases) are termed “tolerators,” while those who show transient liver injury, but adapt are termed “adaptors.” In some subjects, transaminase elevations are a harbinger of a more serious potential outcome. These subjects fail to adapt and therefore are “susceptible” to progressive and serious liver injury, commonly referred to as drug-induced liver injury (DILI). Subjects who experience a transaminase elevation above 3 times the upper limit of normal (\times ULN) should be monitored more frequently to determine if they are an “adaptor” or are “susceptible.”

Liver function tests (LFTs) are not required as a routine safety monitoring procedure in this study. However, should an investigator deem it necessary to assess LFTs because a subject presents with clinical signs/symptoms, such LFT results should be managed and followed as described below.

In the majority of DILI cases, elevations in aspartate aminotransferase (AST) and/or alanine aminotransferase (ALT) precede total bilirubin (Tbili) elevations ($>2 \times$ ULN) by several days or weeks. The increase in Tbili typically occurs while AST/ALT is/are still elevated above $3 \times$ ULN (ie, AST/ALT and Tbili values will be elevated within the same lab sample). In rare instances, by the time Tbili elevations are detected, AST/ALT values might have decreased. This occurrence is still regarded as a potential DILI. Therefore, abnormal elevations in either AST OR ALT in addition to Tbili that meet the criteria outlined below are considered potential DILI (assessed per Hy’s law criteria) cases and should always be considered important medical events, even before all other possible causes of liver injury have been excluded.

The threshold of laboratory abnormalities for a potential DILI case depends on the subject’s individual baseline values and underlying conditions. Subjects who present with the following laboratory abnormalities should be evaluated further as potential DILI (Hy’s law) cases to definitively determine the etiology of the abnormal laboratory values:

- Subjects with AST/ALT and Tbili baseline values within the normal range who subsequently present with AST OR ALT values $>3 \times$ ULN AND a Tbili value $>2 \times$ ULN with no evidence of hemolysis and an alkaline phosphatase value $<2 \times$ ULN or not available.
- For subjects with baseline AST OR ALT OR Tbili values above the ULN, the following threshold values are used in the definition mentioned above, as needed, depending on which values are above the ULN at baseline:
 - Preexisting AST or ALT baseline values above the normal range: AST or ALT values >2 times the baseline values AND $>3 \times$ ULN; or $>8 \times$ ULN (whichever is smaller).

- Preexisting values of Tbili above the normal range: Tbili level increased from baseline value by an amount of at least $1 \times \text{ULN}$ or if the value reaches $>3 \times \text{ULN}$ (whichever is smaller).

Rises in AST/ALT and Tbili separated by more than a few weeks should be assessed individually based on clinical judgment; any case where uncertainty remains as to whether it represents a potential Hy's law case should be reviewed with the sponsor.

The subject should return to the investigator site and be evaluated as soon as possible, preferably within 48 hours from awareness of the abnormal results. This evaluation should include laboratory tests, detailed history, and physical assessment.

In addition to repeating measurements of AST and ALT and Tbili, laboratory tests should include albumin, creatine kinase (CK), direct and indirect bilirubin, gamma-glutamyl transferase (GGT), prothrombin time (PT)/international normalized ratio (INR), total bile acids, alkaline phosphatase and acetaminophen drug and/or protein adduct levels.

Consideration should also be given to drawing a separate tube of clotted blood and an anticoagulated tube of blood for further testing, as needed, for further contemporaneous analyses at the time of the recognized initial abnormalities to determine etiology. A detailed history, including relevant information, such as review of ethanol, acetaminophen (either by itself or as a coformulated product in prescription or over-the-counter medications), recreational drug, supplement (herbal) use and consumption, family history, sexual history, travel history, history of contact with a jaundiced person, surgery, blood transfusion, history of liver or allergic disease, and potential occupational exposure to chemicals, should be collected. Further testing for acute hepatitis A, B, C, D, and E infection and liver imaging (eg, biliary tract) may be warranted.

All cases demonstrated on repeat testing as meeting the laboratory criteria of AST/ALT and Tbili elevation defined above should be considered potential DILI (Hy's law) cases if no other reason for the LFT abnormalities has yet been found. **Such potential DILI (Hy's law) cases are to be reported as SAEs, irrespective of availability of all the results of the investigations performed to determine etiology of the LFT abnormalities.**

A potential DILI (Hy's law) case becomes a confirmed case only after all results of reasonable investigations have been received and have excluded an alternative etiology.

8.4.3. Exposure to the Investigational Product During Pregnancy or Breastfeeding, and Occupational Exposure

Exposure to the investigational product under study during pregnancy or breastfeeding and occupational exposure are reportable to Pfizer Safety within 24 hours of investigator awareness.

8.4.3.1. Exposure During Pregnancy

For both unapproved/unlicensed products and for marketed products, an exposure during pregnancy (EDP) occurs if:

- A female becomes, or is found to be, pregnant either while receiving or having been exposed (eg, because of treatment or environmental exposure) to the investigational product; or the female becomes or is found to be pregnant after discontinuing and/or being exposed to the investigational product.
- An example of environmental exposure would be a case involving direct contact with a Pfizer product in a pregnant woman (eg, a nurse reports that she is pregnant and has been exposed to chemotherapeutic products).
- A male has been exposed (eg, because of treatment or environmental exposure) to the investigational product prior to or around the time of conception and/or is exposed during his partner's pregnancy.

If a subject or subject's partner becomes or is found to be pregnant during the subject's treatment with the investigational product, the investigator must report this information to Pfizer Safety on the CT SAE Report Form and an EDP supplemental form, regardless of whether an SAE has occurred. In addition, the investigator must submit information regarding environmental exposure to a Pfizer product in a pregnant woman (eg, a subject reports that she is pregnant and has been exposed to a cytotoxic product by inhalation or spillage) to Pfizer Safety using the EDP supplemental form. This must be done irrespective of whether an AE has occurred and within 24 hours of awareness of the exposure. The information submitted should include the anticipated date of delivery (see below for information related to termination of pregnancy).

Follow-up is conducted to obtain general information on the pregnancy and its outcome for all EDP reports with an unknown outcome. The investigator will follow the pregnancy until completion (or until pregnancy termination) and notify Pfizer Safety of the outcome as a follow-up to the initial EDP supplemental form. In the case of a live birth, the structural integrity of the neonate can be assessed at the time of birth. In the event of a termination, the reason(s) for termination should be specified and, if clinically possible, the structural integrity of the terminated fetus should be assessed by gross visual inspection (unless pre-procedure test findings are conclusive for a congenital anomaly and the findings are reported).

If the outcome of the pregnancy meets the criteria for an SAE (ie, ectopic pregnancy, spontaneous abortion, intrauterine fetal demise, neonatal death, or congenital anomaly in a live-born baby, a terminated fetus, an intrauterine fetal demise, or a neonatal death), the investigator should follow the procedures for reporting SAEs.

Additional information about pregnancy outcomes that are reported to Pfizer Safety as SAEs follows:

- Spontaneous abortion includes miscarriage and missed abortion;
- Neonatal deaths that occur within 1 month of birth should be reported, without regard to causality, as SAEs. In addition, infant deaths after 1 month should be reported as SAEs when the investigator assesses the infant death as related or possibly related to exposure to the investigational product.

Additional information regarding the EDP may be requested by the sponsor. Further follow-up of birth outcomes will be handled on a case-by-case basis (eg, follow-up on preterm infants to identify developmental delays). In the case of paternal exposure, the investigator will provide the subject with the Pregnant Partner Release of Information Form to deliver to his partner. The investigator must document in the source documents that the subject was given the Pregnant Partner Release of Information Form to provide to his partner.

8.4.3.2. Exposure During Breastfeeding

Scenarios of exposure during breastfeeding must be reported, irrespective of the presence of an associated SAE, to Pfizer Safety within 24 hours of the investigator's awareness, using the CT SAE Report Form. An exposure during breastfeeding report is not created when a Pfizer drug specifically approved for use in breastfeeding women (eg, vitamins) is administered in accord with authorized use. However, if the infant experiences an SAE associated with such a drug's administration, the SAE is reported together with the exposure during breastfeeding.

8.4.3.3. Occupational Exposure

An occupational exposure occurs when, during the performance of job duties, a person (whether a healthcare professional or otherwise) gets in unplanned direct contact with the product, which may or may not lead to the occurrence of an AE.

An occupational exposure is reported to Pfizer Safety within 24 hours of the investigator's awareness, using the CT SAE Report Form, regardless of whether there is an associated SAE. Since the information does not pertain to a subject enrolled in the study, the information is not recorded on a CRF; however, a copy of the completed CT SAE Report Form is maintained in the investigator site file.

8.4.4. Medication Errors and Lack of Efficacy

Other exposures to the investigational product under study may occur in clinical trial settings, such as medication errors and lack of efficacy.

Safety Event	Recorded on the CRF	Reported on the CT SAE Report Form to Pfizer Safety Within 24 Hours of Awareness
Medication errors and lack of efficacy	All (regardless of whether associated with an AE)	Only if associated with an SAE

8.4.4.1. Medication Errors

Medication errors may result from the administration or consumption of the investigational product by the wrong subject, or at the wrong time, or at the wrong dosage strength.

Medication errors include:

- Medication errors involving subject exposure to the investigational product;
- Potential medication errors or uses outside of what is foreseen in the protocol that do or do not involve the participating subject.

Such medication errors occurring to a study participant are to be captured on the medication error page of the CRF, which is a specific version of the AE page.

In the event of a medication dosing error, the sponsor should be notified immediately.

Whether or not the medication error is accompanied by an AE, as determined by the investigator, the medication error is recorded on the medication error page of the CRF and, if applicable, any associated AE(s), serious and non-serious, are recorded on an AE page of the CRF.

Medication errors should be reported to Pfizer Safety within 24 hours on a CT SAE Report Form **only when associated with an SAE**.

8.4.4.2. Lack of Efficacy

Lack of efficacy is reportable to Pfizer Safety only if associated with an SAE.

9. DATA ANALYSIS/STATISTICAL METHODS

Detailed methodology for summarization of the data collected in this trial will be documented in a Statistical Analysis Plan (SAP). The SAP may modify the plans outlined in the protocol; however, any major modifications of significant change to the primary endpoint definition and/or its analysis will also be reflected in a protocol amendment.

As this is an open label study with no comparator, no inferential statistics will be performed. Quantitative variables will be described by standard descriptive statistics (n, mean, standard deviation, minimum, and maximum, 95% confidence intervals), and qualitative variables will be summarized by frequency tables. Summaries will include data for all subjects who took at least one dose of investigational product in this open label extension study.

Baseline values for efficacy, outcomes and special safety endpoints will be the last observation made prior to the subject receiving open label treatment. For safety, for those subjects who were randomized to placebo in the double blind study, baseline values will be the last (pre dose, for ECG and blood pressure/pulse only) observation prior to initiating dosing in the open label extension study normally, the (pre dose, for ECG and blood pressure/pulse only) observation of the last visit in the double-blind study; and for those subjects who were randomized to ziprasidone in the double blind study, baseline values will be the last observation prior to initiating dosing in the double blind study (normally, the value from the Baseline visit in the double blind study).

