3. STUDY DESIGN

This 26 week open label extension study is designed to provide information on the safety and tolerability of oral ziprasidone (20 to 80 mg BID with meals) during long term administration in children and adolescents with Bipolar I Disorder (current or most recent episode manic). It will enroll subjects who have participated in the 4 week, double blind, placebo controlled safety and efficacy trial, Study A1281198, meet study entry criteria, and wish to receive treatment with open label ziprasidone.

The number of subjects entering this open-label trial will be determined by the number of subjects electing to continue treatment after completing or withdrawing from the preceding double blind Study A1281198. We estimate that approximately 55 subjects randomized in the double blind study (based on the increased sample size of N=194 subjects) will be eligible to continue in this open label extension. With an expected dropout rate of approximately 35%, this gives an estimate of approximately 40 subjects to complete this 26 week open label study (if all 55 subjects enter the extension study).

The final visit of the double blind trial (Week 4 or early termination visit from A1281198) will serve as the Baseline Visit for the extension study. The first 1-14 days of Study A1281201 will be considered a transition period during which the study drug will continue to be administered under double-blind conditions. During this double-blind transition period, subjects who were on placebo in Study A1281198 will be provided active medication that will allow them to be titrated up to the appropriate weight-adjusted target dose, following titration schedule that was employed in Study A1281198. Subjects who were on active medication (ziprasidone) at the end of Study A1281198 will continue on that treatment course under double-blind conditions. At the end of the double-blind transition period, all subjects will receive open label ziprasidone.

Any subject who cannot tolerate the transition study medication during Week 1 should be discontinued from the study.

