3.2. Special Safety Endpoints

- *Child Depression Rating Scale - Revised (CDRS-R).*
- *Columbia Suicide Severity Rating Scale (C-SSRS).*
- *Movement Disorder Scales (SARS, BAS, and AIMS).*

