3.4. Baseline Variables

No baseline covariates in the planned analysis.

Baseline visit for the open-label extension study will be the final visit of the double blind trial (Week 4 or early termination visit from A1281198), except for safety ECG parameters. For ECG parameters, baseline values will be the value from the Baseline visit in the double-blind study A1281198.

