4. ANALYSIS SETS (POPULATIONS FOR ANALYSIS)

4.1. Safety Analysis Set

As the objective of the study is long-term safety and tolerability of ziprasidone, only one analysis set, “Safety Analysis Set” defined below will be used for data summaries.

The Safety Analysis Set (SAS) will include *all subjects who took at least one dose of study medication in this open-label extension study.*

All summaries will be based on the “as reported” visits (as recorded on the Case Report Forms).

For data summary purposes, subjects will be classified into one of the following two groups:

- Ziprasidone/Ziprasidone: randomized to ziprasidone in the preceding double-blind study (and on ziprasidone in the current open-label extension study).
- Placebo/Ziprasidone: randomized to placebo in the preceding double-blind study (and on ziprasidone in the current open-label extension study).

In addition, the above two groups will be combined as:

- Combined: combination of the two groups Ziprasidone/Ziprasidone and Placebo/Ziprasidone. This is essentially the set of all subjects in the current open-label extension study.

Data summaries will be done based on Ziprasidone/Ziprasidone and Placebo/Ziprasidone, as well as Combined.

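### For SARS, BAS, AIMS and CDRS-R, baseline is an on-drug value for subjects who had ziprasidone in A1281198, so any change-from-baseline summary leaves out worsening that began there, and Combined pools on-drug with off-drug starting states

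*Protocol*

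**What the plan says.** Protocol section 9 sets two baseline rules in one paragraph. For special safety endpoints, "Baseline values for efficacy, outcomes and special safety endpoints will be the last observation made prior to the subject receiving open label treatment", whatever the prior arm. For the remaining safety data, subjects randomized to ziprasidone are taken back to a value from before the drug: "baseline values will be the last observation prior to initiating dosing in the double blind study".

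SAP 3.2 lists SARS, BAS, AIMS and CDRS-R among the special safety endpoints. SAP 3.4 then says "Baseline visit for the open-label extension study will be the final visit of the double blind trial", with one exception: "For ECG parameters, baseline values will be the value from the Baseline visit in the double-blind study A1281198".

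Subjects from the ziprasidone arm are still taking the drug at that visit and do not wash out. Protocol section 3 says "Subjects who were on active medication (ziprasidone) at the end of Study A1281198 will continue on that treatment course under double-blind conditions". On reporting, SAP 4.1 says "Data summaries will be done based on Ziprasidone/Ziprasidone and Placebo/Ziprasidone, as well as Combined". SAP 6.4 promises descriptive statistics for the scales and does not say whether these are raw scores by visit, changes from baseline, or both.

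**The concern.** The study's only objective is the safety and tolerability of ziprasidone, and these scales are in the endpoint list attached to that objective (Protocol section 2). Suppose akathisia or parkinsonism appears during the parent study's 4 weeks of ziprasidone and then persists. With baseline at extension entry, that subject's change is zero, although the score is worse than before the drug. A prior-placebo subject with the same course shows the full worsening, because it arises after entry. Combined averages the two, so it measures neither change since starting ziprasidone nor further change on continued ziprasidone.

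The adverse event tables may not fill the gap. Under SAP 6.5.1, an event already seen in the double-blind study is treatment emergent only if it later becomes more severe. Protocol 7.3.2 limits the recording of movement disorders as adverse events to clinically meaningful cases. An early, stable movement effect could therefore be missing from both the change scores and the treatment-emergent table.

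**Working it through.** **Step 1: which baseline a prior-ziprasidone subject gets.**

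| Endpoint | Protocol section 9 | SAP 3.4 |
|---|---|---|
| SARS, BAS, AIMS, CDRS-R | before open-label treatment (on drug) | last A1281198 visit (on drug) |
| ECG | before first A1281198 dose | A1281198 Baseline (pre-ziprasidone) |
| Laboratory, vital signs, weight/BMI | before first A1281198 dose | last A1281198 visit (on drug) |

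Taken literally, the Protocol's wording for the scales could mean the end of the double-blind transition, when prior-placebo subjects are also on ziprasidone. SAP 3.4 settles it as the last parent-study visit.

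**Step 2: drug state at that visit.** Ziprasidone/Ziprasidone is on drug. The parent study lasts 4 weeks, and Protocol 4.1 normally requires at least 3 weeks of double-blind treatment, with earlier entry possible for insufficient response. Placebo/Ziprasidone has had no ziprasidone in the parent study. Both groups share one visit rule; what differs is the drug state.

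**Step 3: size.** The documents state no figure for this point, so there is nothing to reproduce. The illustration needs these assumptions:

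- True worsening on ziprasidone, measured from the last pre-ziprasidone value, is 1 unit in every subject of both groups.
- p is the share of subjects with prior ziprasidone, taken as 1/3 to 2/3.
- f is the fraction of the worsening already present at extension entry in those subjects, taken as 0.5 to 1.

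With the planned baseline, the mean changes are:

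- Ziprasidone/Ziprasidone: 1 - f
- Placebo/Ziprasidone: 1
- Combined: p(1 - f) + (1 - p) = 1 - p*f

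| p | Combined, f = 0.5 | Combined, f = 1 |
|---|---|---|
| 1/3 | 0.83 | 0.67 |
| 1/2 | 0.75 | 0.50 |
| 2/3 | 0.67 | 0.33 |

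The shortfall against 1.00 is p*f. It runs from 1/3 × 0.5 = 17% to 2/3 × 1 = 67%. In Ziprasidone/Ziprasidone alone it is f, that is 50% to 100%. If f = 0 there is no shortfall.

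With the last pre-ziprasidone value as baseline, both groups show 1, and Combined is p × 1 + (1 - p) × 1 = 1.00.

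**The case against.** Several points against this stand in part.

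- **Change tables are not specified.** A reader might infer that the plan schedules change scores for these scales. It does not. It names change from baseline for laboratory values and ECG, but not in SAP 6.4. Raw scores by visit would be unaffected. Still, a baseline defined for these endpoints has little other use, so the SAP should say which is meant.
- **There are not two baseline rules for these scales.** One visit applies to everyone. A reader might also infer from the Protocol that the movement scales are singled out; under SAP 3.4 they are not, since only ECG keeps a pre-ziprasidone baseline. The resulting Protocol-SAP conflict for laboratory, weight and vital-sign data is a separate matter.
- **The information is not lost to the programme.** The two groups are reported separately, Placebo/Ziprasidone starts free of ziprasidone, and the placebo-controlled parent study holds the early data. Change from extension entry also answers a fair question about continued treatment, which is a reason to keep it. It does not justify the pooled column.
- **The value before ziprasidone may not be clean.** Table 12 in Protocol 5.9 allows some earlier antipsychotics to stop 10 days or less before baseline, so carry-over or withdrawal effects are possible. The proposed value is pre-ziprasidone, not necessarily drug-free.
- **Selection may lower f.** Entry requires freedom from clinically significant safety concerns in the parent study (Protocol 4.1), which may exclude subjects with marked early worsening.
- **Follow-up would differ.** Change from first dose would span up to about 4 + 26 = 30 weeks in one group and 26 in the other. That should be stated next to the table.

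**Conclusion.** The concern holds in a limited form. For these four scales, a change-from-baseline summary would omit parent-study worsening from Ziprasidone/Ziprasidone and dilute it in Combined, while Placebo/Ziprasidone would be right. This should be changed, because it touches the study's only objective and the remedy is cheap. It does not undermine the study: no test or decision rule depends on these scales.

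The 17% to 67% is conditional on the assumed p and f and on an equal effect in both groups. A reader might take the upper part of that range as the expected understatement of the drug effect. The documents do not support that: the top figure needs the whole worsening to be present at entry and two thirds of subjects to have had prior ziprasidone, and an uncontrolled change is not a drug effect. The case is strongest for SARS, BAS and AIMS. CDRS-R also moves with the course of illness, so early change on drug could go either way. Early onset still matters there, because Protocol 7.3.1 uses the scale to watch for a depressive episode.

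**What to change.** Amend SAP 3.4 and 6.4 as follows:

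1. State whether SARS, BAS, AIMS and CDRS-R are summarized as raw scores, changes, or both.
2. Add change from each subject's last value before the first ziprasidone dose: A1281198 Baseline for Ziprasidone/Ziprasidone, extension entry for Placebo/Ziprasidone. Use this for Combined.
3. Keep change from extension entry as a second column.
4. Note that follow-up from first dose is up to about 4 weeks longer in Ziprasidone/Ziprasidone.

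The cost is one extra column per table and a merge of parent-study baseline data, which SAP 3.4 already requires for ECG. The sponsor must confirm that the scales were rated at the A1281198 Baseline. Protocol 7.6, which lets A1281198 raters use the same scales here, suggests that the parent study used them but does not say at which visits. If a scale was not rated then, the SAP should say so and omit the Combined change for that scale.
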